7.6.4 Safety Evaluations

7.6.4.1 Adverse Event Assessment

The investigator has the responsibility for assessing the safety of the patients and for compliance with the protocol to ensure study integrity. During the screening period, unless otherwise required by local regulations, SAEs which are related to protocol-mandated assessments will be reported. Once enrolled and rucaparib is administered, patients will be monitored for all AEs/SAEs/AESIs during study participation and until 28 days after the last dose of rucaparib. After the 28-day window, only treatment-related SAEs and all AESIs, irrespective of causality, need to be reported. Any ongoing SAEs, AESIs, or treatment-related Grade 3/4 AEs will be followed until resolution or stabilization or until loss to follow-up. AEs and laboratory abnormalities will be graded according to the NCI CTCAE grading system (Version 4.03 or later) and recorded on the eCRF.

Complete details for monitoring AEs, including the definition of drug-related AEs, are provided in [Section 8](#).

7.6.4.2 Clinical Laboratory Investigations

Samples for hematology, serum chemistry, urinalysis, and pregnancy, will be analyzed by a local laboratory. The panels of laboratory tests to be performed are shown below:

Hematology: red blood cell (RBC) count and parameters (hemoglobin, hematocrit, mean corpuscular volume [MCV], mean corpuscular hemoglobin [MCH], and mean corpuscular hemoglobin concentration [MCHC]) and reticulocyte count, white blood cell (WBC) count and differential (with ANC), and platelet count will be assessed at screening, during treatment at each study visit, at the End of Treatment Visit, and 28-day Follow-up Visit for all patients. Hematology results must be reviewed by the investigator before the start of treatment with rucaparib and ongoing at times testing occurs. Additional and more frequent tests may be performed at the investigator's discretion.

Serum Chemistry: total protein, albumin, CrCL or eGFR using the Cockcroft-Gault formula or institutional standard formula, blood urea nitrogen (BUN) or urea, total bilirubin, alkaline phosphatase (ALP), ALT, AST, lactate dehydrogenase (LDH), glucose, sodium, potassium, chloride, carbon dioxide (CO₂), calcium, phosphorus, and total cholesterol, at screening, during treatment at each study visit, at the End of Treatment Visit, and 28-day Follow-up Visit for all patients. Fasting is not required before blood sampling. Serum chemistry results must be reviewed by the investigator before the start of treatment with rucaparib and ongoing at times testing occurs. Additional and more frequent tests may be performed at the investigator's discretion.

Urinalysis: performed locally on a freshly voided clean sample by dipstick for protein, glucose, blood, pH, and ketones. If dipstick findings are abnormal based on the investigator's judgment, then a microscopic evaluation will be performed to assess the abnormal findings. Urinalysis will be performed at screening, during treatment at each study visit, at the End of Treatment Visit, and 28-day Follow-up Visit for all patients, but may be conducted at other times as clinically indicated.

Serum Pregnancy: for women of childbearing potential only. A serum pregnancy test must be performed ≤ 3 days prior to first dose of rucaparib (a negative result is required before dosing can begin) and at the End of Treatment Visit. A serum pregnancy test must be performed ≤ 3 days prior to Day 1 of every cycle during the Treatment Phase. A positive serum pregnancy test during study participation must be reported to the sponsor. Refer to [Section 8.6](#) for details.

Laboratory reports will be reviewed by the investigator or delegated physician who will then comment on out-of-range parameters and assess clinical significance. Clinically significant abnormalities and associated panel results will be documented on the eCRF as an AE. Refer to [Section 8.5](#) for guidelines on reporting of abnormal laboratory values as AEs.

7.6.4.3 Vital Signs

Vital signs will include blood pressure, pulse, and body temperature and will be taken after the patient has been resting for at least 5 minutes during screening, at study visits during the Treatment Phase, at the End of Treatment Visit, and the 28-day Follow-up Visit.

7.6.4.4 12-Lead Electrocardiogram

For all patients, 12-lead ECGs will be performed at the following times:

- Screening (within 28 days prior to enrollment)
- End of Treatment Visit

The following will be measured or calculated: heart rate, PR, QRS, QT, and rhythm. The investigator or qualified designee will review the ECGs locally and assess the results as normal or abnormal (clinically significant or not clinically significant).

If it is clinically indicated, ECGs can be performed at other times during the study.

7.6.4.5 Body Weight and Height

Height will be measured during the screening visit only. Weight will be measured per institutional guidelines during screening, during treatment at each study visit, at the End of Treatment Visit, and at the 28-day Follow-up visit.

7.6.4.6 Physical Examinations

Physical examinations will include an assessment of all the major body systems. Complete physical examinations will be performed during screening and at treatment discontinuation. Physical examinations at study visits during the Treatment Phase and 28-day Follow-up Visit will be limited as appropriate.

7.6.4.7 ECOG Performance Status

ECOG performance status ([Appendix 2](#)) will be assessed during screening, at study visits during the Treatment Phase, at the End of Treatment Visit, and at the 28-day Follow-up Visit.

The ECOG performance status should be assessed by the same study personnel at each visit, if possible. For eligibility purposes, patients with borderline ECOG performance status should be considered carefully to avoid enrolling patients who may have significant impairment.

7.6.5 Biomarker Analysis – Tumor Tissue

7.6.5.1 Biomarker Analysis – Mandatory Tumor Tissue Collection

Submission of pre-treatment tumor tissue is mandatory, and defined as a biopsy or surgical specimen obtained prior to the first dose of rucaparib from a primary or metastatic soft tissue tumor lesion that has not been previously irradiated. Ascites is not an acceptable specimen for the tumor tissue requirement. If tumor tissue was collected within 6 months of the first dose of rucaparib and no intervening anti-cancer treatments were administered during this period, this tissue may be submitted for the pre-treatment tumor tissue requirement. The tumor tissue should be of adequate quality for molecular profiling and be provided in the form of an FFPE block or unstained slides (see Pathology Charter). The required pre-treatment tumor tissue should be submitted to the sponsor's laboratory by Cycle 2 Day 1 of study treatment, and an associated pathology report should accompany each tumor sample specimen.

The submitted tumor samples will undergo central HRD testing in order to assess each participant's HRD tumor status by NGS molecular profiling. If an actionable mutation, as defined by the American College of Medical Genetics and Genomics (<https://www.ncbi.nlm.nih.gov/clinvar/docs/acmg/>), is detected from this testing, the finding will be made available to the investigator provided the results are generated from a CLIA-certified laboratory and the patient has consented to receive the results.

Additional genomic, transcriptional, or epigenetics assays may also be performed on available specimens to understand the genomics of bladder cancer, as well as molecular factors driving the response and resistance to rucaparib.

7.6.5.2 Biomarker Analysis – Archival Biopsy

Archival FFPE tumor tissue must be submitted if available. There is no age limit to these samples. If available, a pathology report should be included with the specimen. Sample details will be provided in the Pathology Charter.

These samples will be used for molecular profiling to understand the genomics of bladder cancer, as well as the evolution and impact of intervening therapies on molecular drivers of rucaparib sensitivity.

7.6.5.3 Biomarker Analysis – Optional Biopsy after progression

End of treatment and/or upon progression tumor biopsies are not mandatory, but their collection is strongly encouraged, and will be used for molecular profiling to determine potential mechanisms of resistance to rucaparib. Patients must provide additional consent for the optional tumor tissue biopsy sample. New lesions or lesions that are growing should be

prioritized for the optional biopsy. If possible, collect the lesion responsible for progression. Sample collection details will be provided in the Pathology Charter.

7.6.6 Biomarker Analysis – ctDNA from Blood

Blood samples for plasma ctDNA will be collected during screening, before dosing on Day 1 of Cycles 1, 2, 3, and at every 8 weeks thereafter coinciding with radiographic scans, and at the end of treatment discontinuation from all patients entered in the study. Sample collection details will be provided in the Laboratory Manual.

These samples will be used for ctDNA profiling to assess alterations in genes that may be associated with response and resistance to rucaparib.

7.6.7 Biomarker Analysis - Genomic DNA from Blood

A blood sample for genomic analysis will be collected at Cycle 1 Day 1 from all patients. Sample collection details will be provided in the Laboratory Manual.

Genomic DNA may be purified and tested to determine whether any mutations identified from NGS tissue testing are of germline origin. Because the germline analysis will be done near the end of the study, there are no plans to share these results with the investigator and the patient. However, if an actionable mutation, as defined by the American College of Medical Genetics and Genomics (<https://www.ncbi.nlm.nih.gov/clinvar/docs/acmg/>), is detected, these incidental finding will be made available to the investigator provided the results are generated from a CLIA-certified laboratory and the patient has consented to receive the results.

7.6.8 Pharmacokinetics Evaluation

Plasma samples are to be collected for trough level PK analysis of rucaparib 1 hour before the morning dose on Cycle 2 Day 1, Cycle 3 Day 1, and Cycle 4 Day 1. If the start of the next dose is postponed or suspended, the PK sample should be collected as close as possible to 12 hours after the previous dose. Refer to the Laboratory Manual for sample collection details for PK samples.

8 ADVERSE EVENT MANAGEMENT

8.1 Definition of an Adverse Event

An AE is defined as any untoward medical occurrence in a patient administered a medicinal product that does not necessarily have a causal relationship with this treatment. An AE can, therefore, be any unfavorable and unintended sign (including an abnormal laboratory finding), symptom, or disease temporally associated with the use of an investigational product, whether or not related to the investigational medicinal product. This includes an exacerbation of pre-existing conditions or events, intercurrent illnesses, drug interaction, or the significant worsening of the indication under investigation that is not recorded elsewhere on the eCRF under specific efficacy assessments. Anticipated fluctuations of pre-existing conditions, including the disease under study, that do not represent a clinically significant exacerbation or worsening, are not considered AEs.

It is the responsibility of the investigator to document all AEs that occur during the study. AEs should be elicited by asking the patient a non-leading question (eg, “Have you experienced any new or changed symptoms since we last asked/since your last visit?”). The existence of an AE may be concluded from a spontaneous report of the patient; from the physical examination; or from special tests such as the ECG, laboratory assessments, or other study-specified procedure (source of AE). Symptoms reported spontaneously by the patient during the physical examination would also qualify as an AE (and hence documented on the AE eCRF, not on the physical examination eCRF, which is reserved for physical signs or findings).

8.2 Definition of a Serious Adverse Event

An SAE is any untoward medical occurrence that occurs at any dose (or, occurs after informed consent is given and prior to dosing if the SAE is related to a study procedure) that:

- Results in death. Any event resulting in death during the reporting period (from date of first dose of rucaparib through 28 days after last dose) must be treated as an SAE and reported as such. An event related to a study procedure that occurs after informed consent, but prior to dosing, that results in death must also be reported as an SAE.
- Is life-threatening (patient is at immediate risk of death from the event as it occurred)
- Requires in-patient hospitalization (formal admission to a hospital for medical reasons) or prolongation of existing hospitalization
- Results in persistent or significant disability/ incapacity
- Results in a congenital anomaly or birth defect
- Important medical events that may not result in death, are not life-threatening, or do not require hospitalization may be considered SAEs when, based on appropriate medical judgment, they may jeopardize the patient and may require medical or surgical intervention to prevent 1 of the outcomes listed in this definition. Examples of such events include allergic bronchospasm requiring intensive treatment in an emergency room or at home or the development of drug dependency or drug abuse.

8.3 Definition of an Adverse Event of Special Interest

AESIs (serious or nonserious) are defined as AEs of scientific and medical concern specific to the sponsor's product or program, for which ongoing monitoring and rapid communication by the investigator to the sponsor can be appropriate. Such an event might warrant further investigation in order to characterize and understand it. Depending on the nature of the event, rapid communication by the trial sponsor to other parties (eg, regulators) might also be warranted.

Details on the sponsor's currently agreed list of AESIs for rucaparib can be found in the current rucaparib IB. These AESIs are to be reported to the sponsor within 24 hours (see [Section 8.9](#) for reporting instructions).

8.4 Events or Outcomes Not Qualifying as Serious Adverse Events

The following are not considered SAEs and therefore do not need to be reported as such:

- Preplanned or elective hospitalization including social and/ or convenience situations (eg, respite care)
- Hospital visits of less than 24-hours duration (eg, patient presents to the emergency room, but is not admitted to a ward)
- Overdose of either rucaparib or concomitant medication unless the event meets SAE criteria (eg, hospitalization). However, the event should still be captured as a nonserious AE on the appropriate eCRF page.
- Events of progression of the patient's underlying cancer as well as events clearly related to progression of the patient's cancer (signs and symptoms of progression) should not be reported as an AE/SAE.
- Events that meet the SAE criteria (as outlined in [Section 8.2](#)) and occur after informed consent, but before the first dose of rucaparib, which are considered unrelated to screening procedures.

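### Protocol 8.4 excludes hospital visits under 24 hours from SAEs without making that exclusion subject to the seriousness criteria in 8.2

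*Protocol*

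**What the plan says.** Section 8.2 of the protocol makes an event serious if it meets any one of its criteria. Three matter here:

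- The life-threatening criterion, which refers to immediate risk of death and not to where or how long the patient is treated.
- The hospitalization criterion: "Requires in-patient hospitalization (formal admission to a hospital for medical reasons) or prolongation of existing hospitalization". It sets no minimum stay.
- The important-medical-event criterion, which is left to medical judgment and covers events that may not require hospitalization. One of its examples is "allergic bronchospasm requiring intensive treatment in an emergency room".

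Section 8.4 then gives a list introduced by: "The following are not considered SAEs and therefore do not need to be reported as such". The second item is: "Hospital visits of less than 24-hours duration (eg, patient presents to the emergency room, but is not admitted to a ward". It has no qualifying clause. The item after it does: "Overdose of either rucaparib or concomitant medication unless the event meets SAE criteria (eg, hospitalization".

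Three things use the classification. Protocol 8.9 requires SAEs to reach the sponsor within 24 hours and, after the 28-day window, limits reporting to treatment-related SAEs and all AESIs. It also ties the sponsor's regulatory reports to events that are both serious and unexpected. Protocol 9.7.1 and SAP 11.1 tabulate serious TEAEs.

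**The concern.** Section 8.4 uses a duration test, under 24 hours. Section 8.2 uses formal admission for hospitalization, and for its other criteria looks at the nature of the event. Neither section says which prevails when the tests disagree. A site that treats the 8.4 list as final would class some short-visit events as non-serious; a site that starts from 8.2 would class the same events as serious. With about 65 sites planned (Protocol 4.1), both readings could be in use together.

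Any error from the literal 8.4 reading runs one way, because the list can only remove events from the SAE category. During treatment, the result is a non-expedited event and a missing entry in the serious-TEAE tables. After the 28-day window, a treatment-related event classed as non-serious, and not an AESI, would not be reported at all. The safety data reviewed by the DMC (Protocol 11.6) would carry the same classification.

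**Working it through.** No sample size, power or event count enters this point, so there is no figure to reproduce. The check is to take each kind of short visit through both sections as written.

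1. **Life-threatening event, managed in under 24 hours without ward admission.** Under 8.2 it is serious. Under the literal wording of 8.4 it is not. The two agree only if 8.4 is read as describing the visit and not the event treated during it.

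2. **Allergic bronchospasm treated intensively in an emergency room, discharged the same day.** Section 8.2 says such an event may be considered serious on medical judgment and offers it as an example. It also fits the example in 8.4 of a patient seen in the emergency room and not admitted. Section 8.2 permits the serious classification; 8.4, read literally, forbids it.

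3. **Formal admission lasting under 24 hours.** Under 8.2 it is serious, since no minimum stay is set. The opening words of the 8.4 item could exclude it on duration, but the example concerns a patient who was not admitted. The result is unclear.

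4. **Ordinary emergency-room visit, no admission, no other criterion met.** Not serious under either section. No conflict.

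Reporting then follows from the classification:

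- *Through 28 days after the last dose:* all AEs go on the AE eCRF (Protocol 8.7), so a case 1 or case 2 event is recorded. If classed as non-serious and not an AESI, it is outside the 24-hour duty in 8.9 and outside the serious-TEAE tables.
- *After 28 days:* only treatment-related SAEs and AESIs are reported (Protocol 8.7 and 8.9). A related case 1 event classed under 8.4, and not an AESI, has no reporting route. The TEAE tables are not affected here, because TEAEs end 28 days after the last dose.

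**The case against.** The best defence is that the sections can be reconciled without an edit. Section 8.2 defines hospitalization as formal admission, and the 8.4 item can be read as saying only that a short visit without admission does not meet that criterion. The important-medical-event criterion is written for events that may not need hospitalization, so 8.2 already expects SAEs in patients who are not admitted. Protocol 8.7 asks for each AE to be assessed for seriousness. The missing clause is not decisive either. The item on elective hospitalization also lacks one, and it would be strained to read it as making a life-threatening event during a planned admission non-serious. Overdose may carry the clause because overdose is itself the event.

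Much of this stands. It is the likely intent, and it rules out one stronger inference. A reader might take the final item of 8.4, beginning "Events that meet the SAE criteria (as outlined in" and dealing with unrelated events before the first dose, as proof that the list overrides 8.2. It is not: the opening of 8.2 itself limits pre-dose SAEs to those related to a study procedure, so the two agree.

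It is also fair that on-treatment events are not lost. They appear in the general TEAE tables, including those by grade and for Grade 3 or higher, and AESIs go to the sponsor within 24 hours whether serious or not.

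What the defence does not supply is text. The benign reading has to be inferred from an introduction that says without qualification that the listed items are not SAEs, and from an item whose stated test is duration.

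**Conclusion.** The point holds as a wording gap with a real reporting consequence. Section 8.4 does not make its short-visit exclusion subject to 8.2. Applied as written, it gives the wrong answer for life-threatening events, removes a judgment that 8.2 leaves to the investigator, and leaves admissions under 24 hours undecided.

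Three stronger readings are tempting and are not supported:

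- That 8.2 makes every emergency-room-treated event an SAE. It does not; that criterion is discretionary, and its example specifies intensive treatment.
- That the sections flatly contradict each other on formal admissions. They do not; the example in 8.4 is a patient not admitted, so this is an ambiguity.
- That the serious-TEAE rate would shift by a stated number of points. The documents give neither the frequency of short-visit events meeting an 8.2 criterion nor the proportion of sites that would follow 8.4 literally. Any figure would simply restate an assumption.

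The direction can be stated: under-reporting of SAEs if 8.4 is followed literally. The conclusion assumes only that some sites would do so. It does not touch ORR or the futility rules, which use response counts.

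**What to change.** Reconcile the two sections in the 8.4 item. After the words on duration, add: *without formal admission, unless the event meets any SAE criterion in Section 8.2*. The first part settles short admissions in line with the admission test in 8.2. The second gives short visits the same exception as overdose ("unless the event meets SAE criteria (eg, hospitalization") and leaves 8.2 as the single definition of seriousness. No change to the SAP is needed, since its serious-TEAE tables take the classification as recorded.

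The cost is one clause in a protocol amendment, a few more SAE forms and a slightly higher SAE count. If the sponsor already intends the benign reading, the edit only puts it in writing.

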8.5 Clinical Laboratory Assessments as Adverse Events and Serious Adverse Events

It is the responsibility of the investigator to assess the clinical significance of all abnormal values as defined by the list of reference ranges from the local laboratory. In some cases, significant changes in lab values within the normal range will require similar judgment.

An abnormal laboratory value that is not already associated with an AE is to be recorded as an AE only if any 1 of the following criteria is met:

- an action on rucaparib treatment is made as a result of the abnormality
- intervention for management of the abnormality is required
- at the discretion of the investigator should the abnormality be deemed clinically significant

8.6 Pregnancy or Drug Exposure during Pregnancy

If a patient becomes pregnant during the course of the study, rucaparib dosing should be held immediately.

Pregnancy is not considered to be an AE or SAE; however, all pregnancies occurring during study participation or within 6 months of last dosing must be reported to the sponsor using the Pregnancy Report Form within the same timelines as for an SAE.

All pregnancies should be followed through to outcome. Once the outcome of a pregnancy is known, the Pregnancy Outcome Report Form should be completed and submitted to the sponsor.

AEs, SAEs, or AESIs that occur during pregnancy will be assessed and processed according to the AE or SAE/ AESI processes using the appropriate AE or SAE/ AESI forms.

8.7 Recording of Adverse Events, Serious Adverse Events, and Adverse Events of Special Interest

Events that occur after signing of informed consent, but prior to initiation of rucaparib, unless due to a protocol-mandated procedure, will be recorded on the Medical History eCRF. Any event related to a protocol-mandated procedure should be reported during the screening period. Any AE that occurs after first dose of rucaparib through 28 days after receiving the last dose of rucaparib will be recorded on the AE eCRF. After the 28-day reporting window after discontinuation of rucaparib treatment, only SAEs assessed as related to rucaparib and all AESIs, irrespective of causality, need to be reported. Information on the follow-up of AEs, SAEs, and AESIs is provided in [Section 8.8](#).

In order to avoid vague, ambiguous, or colloquial expressions, the AE should be recorded in standard medical terminology rather than the patient's own words. Whenever possible, the investigator should combine signs and symptoms that constitute a single disease entity or syndrome into a final diagnosis, if appropriate. For example, fever, cough, and shortness of breath may be reported as pneumonia, if that is a reasonable diagnosis.

Each AE is to be evaluated for **causal relationship**, severity, and seriousness to the investigational drug. The action taken and the outcome must also be recorded.

SAEs and AESIs that occur during the study or within 28 days after receiving the last dose of rucaparib, whether or not related to rucaparib, must be reported immediately (ie, **within 24 hours** of knowledge of the event or additional information for a previously reported event) to the sponsor/ SAE designee. The contact information for reporting of SAEs/AESIs can be found on the SAE/AESI Reporting Form.

